4.1.2 Arm 2 Part I: Dose Escalation in Metastatic Visceral Lesion Tumors

In Arm 2 Part I of the study, an mTPI design will be used to identify and confirm the RP2D of V937. Three predetermined dose levels of V937 will be evaluated:

Dose level 1: 3×10^7 (3E7) TCID₅₀

Dose level 2: 1×10^8 (1E8) TCID₅₀

Dose level 3: 3×10^8 (3E8) TCID₅₀

The number of participants enrolled per dose level during dose escalation will be based on the occurrence of DLTs per the mTPI design. The maximum RP2D will be capped at 3E8. The administered dose is dependent on the volume of tumor injected (see [Table 10](#) and [Table 11](#)). V937 will be administered ITu on Days 1 and 8 of Cycle 1 (28 days), then Day 1 of Cycle 2 through Cycle 8, for a maximum of 9 doses. The dose of pembrolizumab will remain constant at 200 mg IV every 21 days for a maximum of 35 treatment cycles (approximately 2 years).

In Arm 2 Part I only, each of the first 3 participants in DL1 will undergo an observation period of 5 days before the next participant is dosed. Subsequent participants in all other dose levels will not undergo a staggered enrollment. Dose-finding and confirmation in Arm 2 Part I will end after 14 participants have been treated at any of the selected doses, per mTPI design. The pool-adjacent violators algorithm will be used to estimate the DLT rates across doses in each treatment arm under the assumption of monotonicity between DLT rates and dose levels [Ji, Y. and Wang, S.-J. 2013]. The dose with an estimated DLT rate closest to 30% may be treated as a preliminary RP2D. The totality of the data will be considered before deciding on the dose to carry forward to Arm 2 Part II.

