6.3 Measures to Minimize Bias: Randomization and Blinding

6.3.1 Intervention Assignment

Intervention allocation will occur centrally using an IVRS/IWRS. Participants will be assigned to 1 of 2 treatment arms.

Study intervention will be allocated by nonrandom assignment in both treatment arms. Arm 1 and Arm 2 Part I will undergo simultaneous enrollment. Investigator assessment of eligibility and tumor type will guide participant allocation to Arm 1 or Arm 2 Part I. In Arm 2 Part I only, each of the first 3 participants in DL1 will undergo an observation period of 5 days before the next participant is dosed. All other participants enrolled (Arm 1; Arm 2 Part I participant 4 and greater; Arm 2 Part I dose levels 2 and 3; Arm 2 Part II) will not be staggered. Each new dose level will open for enrollment without delay once the 28-day DLT observation period of the previous dose level is completed and a dose escalation decision is made.

Arm 2 Part II will begin enrollment once the participants in Arm 2 Part I complete the DLT evaluation and a RP2D decision has been made; IVRS/IWRS will assign participants to 1 of 2 cohorts by tumor type.

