6.6.5 Definition of Dose-limiting Toxicity for Arm 2 Part I (mTPI Escalation)

Dose-limiting toxicities are used in Arm 2 Part I to guide dose escalation and de-escalation decisions for the mTPI design (see Section 4.3.1.3). The DLT window of observation will be during Cycle 1.

All toxicities will be graded using NCI-CTCAE v5.0 based on the investigator assessment.

The occurrence of any of the following toxicities during Cycle 1 will be considered a DLT, if assessed by the investigator to be possibly, probably, or definitely related to study intervention administration.

1. Grade 4 nonhematologic toxicity (not laboratory).
2. Grade 4 hematologic toxicity lasting ≥ 7 days except for thrombocytopenia or febrile neutropenia:
 - \geq Grade 3 thrombocytopenia associated with clinically significant bleeding of any duration, or
 - Any grade of febrile neutropenia
3. Any nonhematologic AE \geq Grade 3 in severity should be considered a DLT, with the following exceptions: Grade 3 fatigue lasting ≤ 3 days; Grade 3 diarrhea, nausea, or vomiting without use of anti-emetics or anti-diarrheals per SOC; clinically asymptomatic Grade 3 elevations of amylase or lipase without any imaging evidence suggestive of possible/probable etiology; Grade 3 rash without use of corticosteroids or anti-inflammatory agents per SOC.
4. Any Grade 3 or Grade 4 nonhematologic laboratory value if:
 - Clinically significant medical intervention is required to treat the participant, or
 - The abnormality leads to hospitalization, or
 - The abnormality persists for >1 week, or
 - The abnormality results in a DILI (see Section 8.4.7 for criteria).Exceptions: Clinically nonsignificant, treatable, or reversible laboratory abnormalities including liver function tests, uric acid, etc.
5. Prolonged delay (>2 weeks) in initiating Cycle 2 due to intervention-related toxicity.
6. Any intervention-related toxicity that causes the participant to discontinue intervention during Cycle 1.
7. Missing the following number of ITu V937 doses as a result of drug-related AE(s) during the first cycle:
 - Visceral tumor, dose escalation: missing 1 dose of V937
8. Grade 5 toxicity.

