6.6.6 Guidelines for Dose Modification due to Adverse Events

6.6.6.1 Dose Modification for V937 and/or Pembrolizumab due to Drug-related AEs in Arm 2 Part I

The CTCAE v5.0 must be used to grade the severity of AEs. The investigator may attribute toxicity events to the combination of V937 and pembrolizumab (since one may not be able to separate individual drug effects in every circumstance) and modify the dose according to [Table 17](#). If a dose modification for toxicity occurs with V937, the dose may not be re-escalated to the dose that preceded the dose modification. Dose modifications are always based on the previous cycle.

Reduction or holding of 1 agent and not the other agent is appropriate if, in the opinion of the investigator, the toxicity is clearly related to 1 of the study interventions. For example, if V937 is held due to an AE attributed to that drug, then pembrolizumab may continue to be administered. Appropriate documentation is required regarding to which drug the investigator is attributing the adverse event. If, in the opinion of the investigator, the toxicity is related to the combination of 2 agents, then both drugs should be held according to recommended dose modifications.

The dose of V937 may be decreased during Arm 2, Part I (as described in [Table 17](#)). Participants may receive up to 2 dose modifications of V937 during the dose escalation phase, provided this reduction is not lower than that specified in DL1 ([Table 13](#)). If a dose reduction is needed from DL1, then V937 treatment should be discontinued. If further toxicity occurs, or criteria for resuming treatment are not met, then the participant must also be discontinued from study. If a participant experiences several toxicities which result in conflicting therapeutic regimens, then the treating physician should adhere to the most conservative dose adjustment recommended (ie, adjustment based on the severest AE reported). There will be no V937 dose reductions in Arm 1 or Arm 2, Part II.

Exceptional circumstances to the dose modification tables may be considered after consultation with the Sponsor.

Table 17 V937 Dose Modification and Treatment Discontinuation Guidelines for Drug-related Adverse Events in Arm 2, Part I (mTPI)

Toxicity	Hold Treatment	Criteria for Restarting Treatment	V937 Dose for Restarting Treatment	Criteria for Discontinuation after Consultation with Sponsor
Hematological toxicities:				
• Any Grade 1 hematological toxicity	No	N/A	N/A	N/A

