• Any Grade 2 hematological toxicity, or Grade 3 toxicity that persists for \leq 5 days	Per medical assessment of the investigator	If treatment held, may be restarted when AE resolves back to baseline or to Grade 1.	Per medical assessment of the investigator: may decrease dose by 1 dose level.	If AE persists for 12 weeks without resolution following reduction in dose
• Any Grade 3 hematologic toxicity that persists for $>$ 5 days, or Grade 4 hematological toxicity • Febrile neutropenia • Grade 3 thrombocytopenia of any duration if associated with bleeding	Yes	Treatment may be restarted when AE resolves back to baseline or to Grade 1.	Decrease dose by 1 dose level.	If AE persists for 12 weeks without resolution following reduction in dosing schedule. Permanent discontinuation should be considered for any severe or life-threatening event
Nonhematological toxicities:				
• Any Grade 1 nonhematological toxicity • Grade 2 alopecia • Grade 2 fatigue	No	N/A	N/A	N/A
• Any Grade 2 nonhematological toxicity except Grade 2 alopecia and Grade 2 fatigue	Per medical assessment of the investigator	If treatment held, may be restarted when AE resolves back to baseline or to Grade 1.	Per medical assessment of the investigator: may decrease dose by 1 dose level.	If AE persists for 12 weeks without resolution following reduction in dose.
• Any Grade 3 or 4 nonhematological toxicity (not including laboratory, unless clinically significant medical intervention is required to treat the participant, or the abnormality leads to hospitalization, or the abnormality persists for $>$ 1 week)	Yes	Treatment may be restarted when AE resolves back to baseline or to Grade 1.	Decrease dose by 1 dose level.	If AE persists for 12 weeks without resolution following reduction in dose. Permanent discontinuation should be considered for any severe or life-threatening event

In case toxicity does not resolve to Grade 0-1 within 12 weeks after last intervention, V937 should be discontinued after consultation with the Sponsor.

With investigator and Sponsor agreement, participants with a laboratory AE still at Grade 2 after 12 weeks may continue intervention in the study only if asymptomatic and controlled.

After any Grade 4, drug-related AE, participants should not restart study intervention without consultation with the Sponsor. Toxicity must have resolved to Grade 0-1 or baseline prior to restarting.

Pembrolizumab treatment will be modified for the irAEs described in Section 6.6.2.

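### The 28-day DLT period in Arm 2 Part I ends 16 to 21 days before DLT item 5 (delayed Cycle 2) can be known, so escalation may be decided without it

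*Combined protocol and SAP*

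**What the plan says.** Section 6.6.5 (DLT definition for Arm 2 Part I): "The DLT window of observation will be during Cycle 1". Its lead-in counts listed toxicities occurring in that cycle. Item 5 of the list is a delay of more than 2 weeks "in initiating Cycle 2 due to intervention-related toxicity".

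Section 6.3.1: each new dose level opens "without delay once the 28-day DLT observation period of the previous dose level is completed and a dose escalation decision is made".

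Section 4.1.2: in Part I, "each of the first 3 participants in DL1 will undergo an observation period of 5 days before the next participant is dosed". Beyond that, "Subsequent participants in all other dose levels will not undergo a staggered enrollment".

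Section 6.6.6.1 allows one agent to be held without the other: "if V937 is held due to an AE attributed to that drug, then pembrolizumab may continue to be administered". It also says: "If a dose reduction is needed from DL1, then V937 treatment should be discontinued". Tables 14 and 17 list the toxicities for which pembrolizumab or V937 is held.

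Section 6.6.5 refers to Section 4.3.1.3 for the mTPI decisions. That section and Table 6 (the dose-finding rules) are redacted in the public version.

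**The concern.** A DLT observation period should be long enough to observe every event on the DLT list. Item 5 is defined by something that happens after Cycle 1 ends, yet the visible text treats the period as complete at Day 28. A participant whose Cycle 2 is on hold for toxicity at that point, and who meets no other item, has finished Cycle 1 without a recorded DLT. That fits the example of a DLT-evaluable participant in Section 9.5.1.

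At stake is one escalation step (DL1 to DL2, or DL2 to DL3) taken before a DLT at the lower dose is known. Section 4.3.1.1 says V937 has not previously been injected into visceral tumors. The nominal steps are 1×10⁸ / 3×10⁷ = 3.3-fold and 3×10⁸ / 1×10⁸ = 3-fold.

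**Working it through.** **1. The plan's own figure.** Cycle 1 in Arm 2 Part I is Days 1 to 28 (Section 4.1.2, Table 3). This agrees with the 28-day DLT period in Section 6.3.1.

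**2. When item 5 can first be met.**
- Cycle 2 Day 1 is scheduled on Day 28 + 1 = 29.
- A delay of exactly 2 weeks ends on Day 29 + 14 = 43, so more than 2 weeks is first reached on Day 44. The gap after Day 28 is 44 − 28 = 16 days.
- Table 3 allows Cycle 2 dosing up to 5 days either side of the scheduled day. Counted from the late end: 29 + 5 = 34, then 34 + 15 = 49, a gap of 21 days.
- Even counted from the early end (29 − 5 = 24, then 24 + 15 = 39), item 5 falls after Day 28.

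**3. Does the stagger close the gap?** At the minimum 5-day spacing, the first three DL1 participants are dosed on calendar days 1, 6 and 11. The third reaches Day 28 on calendar day 38, when the three are at study Days 38, 33 and 28. They are 44 − 38 = 6, 44 − 33 = 11 and 44 − 28 = 16 days short of Day 44. At DL2 there is no stagger, so all three can be at Day 28 together.

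**4. Is item 5 redundant?** Compare the hold rules with the rest of the DLT list.
- Item 7 makes one missed V937 dose in Cycle 1, if due to a drug-related AE, a DLT. V937 is given on Days 1 and 8, so item 7 catches a toxicity that stops the Day 8 dose. It does not catch one arising afterwards. Pembrolizumab is first given on Day 8, so its immune-related events will generally come too late for item 7.
- Table 17 requires a hold for "Any Grade 3 hematologic toxicity that persists for" more than 5 days. Under item 2, Grade 3 hematologic toxicity is a DLT only as thrombocytopenia with clinically significant bleeding or as febrile neutropenia.
- Table 17 also allows discretionary holds for Grade 2 toxicity (not for Grade 2 fatigue or alopecia), and Table 14 requires pembrolizumab to be withheld for several Grade 2 immune-related events. DLT items 3 and 4 start at Grade 3.
- At DL1 a required dose decrease means stopping V937, so some of these cases may already count under item 6 if the stop falls in Cycle 1.

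Item 5 is therefore the only route to a DLT for a toxicity that leaves Day 8 dosing intact, meets no other item, and still blocks Cycle 2 on Day 44.

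**5. Could one late DLT change a decision?** Table 6 is redacted, so this is an illustration under assumed conventional mTPI settings: target 30%, Beta(1,1) prior, interval 0.25 to 0.35, overdose cut-off 0.95. The decision is the interval with the largest posterior probability per unit length.
- 0 of 3 DLTs, posterior Beta(1,4): below 0.25, (1 − 0.75⁴)/0.25 = 0.684/0.25 = 2.73; within, (0.75⁴ − 0.65⁴)/0.10 = 0.138/0.10 = 1.38; above, 0.65⁴/0.65 = 0.27. Escalate.
- 1 of 3 DLTs, posterior Beta(2,3): below, 0.262/0.25 = 1.05; within, 0.175/0.10 = 1.75; above, 0.563/0.65 = 0.87. Stay.

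The decisions are the same with an interval of 0.27 to 0.33. With six participants under these settings, 1 of 6 escalates and 2 of 6 stays, but 0 of 6 and 1 of 6 both escalate. A late DLT matters only at a boundary.

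**The case against.** The strongest reply is that Section 6.3.1 fixes no decision date. It sets two conditions, a completed period and a decision, and the prompt opening follows both. The study is open-label, a Cycle 2 hold is visible from about Day 29, and nothing tells the sponsor to ignore it. This stands: a reader might infer that the plan obliges escalation at Day 28, but the text gives only an earliest point and leaves room to wait. Section 9.5.1 does not change that, because it describes an analysis population by example and is not an escalation rule.

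The second reply is that the dose-finding rules are redacted and a rule for pending participants would naturally sit there. This also stands, so it cannot be said that the plan lacks one. What remains is that the visible Sections 6.3.1 and 6.6.5 describe a 28-day period that cannot contain item 5.

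The third reply is that the lasting consequence is small. A late DLT enters the cumulative count, the dose carried into Part II is chosen on all the data (Section 4.1.2), and the final RP2D uses all available safety information (Section 4.1). This is fair. A reader might infer a biased RP2D, but the documents do not support that. The exposure is a possible early step, and only two upward steps exist.

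**Conclusion.** The point holds, as a minor one. The 28-day period cannot capture a listed DLT, and escalation may be decided 16 to 21 days before that DLT is known. The day counts rest only on the protocol's schedule; the spread depends on whether the delay runs from the scheduled day or from the end of the window.

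The number of participants who would depend on item 5 alone is unknown. It is tempting to turn this into an increased probability of escalating. The documents do not support such a figure, because they give neither the share of DLTs that would be item 5 only nor the visible mTPI settings. The illustration in the working shows only that one late DLT can matter at a boundary.

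A strictly literal reader might also infer that item 5 can never count, since the delay occurs after Cycle 1. The more natural reading is that it counts as the consequence of a Cycle 1 toxicity, which is why it is listed. A related ambiguity is real: the visible text does not say whether giving one agent while the other is held starts Cycle 2, so it is unclear when item 5 applies.

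**What to change.** In Section 6.6.5, state that item 5 is assessed beyond Day 28 for toxicity arising in Cycle 1 and counts as a Cycle 1 DLT. Say whether pembrolizumab alone, with V937 held, starts Cycle 2, and likewise V937 alone under a Table 14 hold.

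In Section 6.3.1, state that a participant on a toxicity hold at Day 28 is pending, and that escalation waits until Cycle 2 starts or the 2-week limit has passed. If Section 4.3.1.3 already says this, align Sections 6.3.1 and 6.6.5 with it by cross-reference.

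The cost is a few sentences and a wait of about 16 to 21 days, incurred only when such a hold exists. A participant who starts Cycle 2 on schedule is cleared of item 5 at about Day 29 and needs no extended wait.

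Because the study is being discontinued, the practical use may be mainly in reporting. The DLT rate at the RP2D required by Section 9.6.2 should be derived with item 5 fully observed, and any escalation decided before that should be flagged.

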6.6.6 Guidelines for Dose Modification due to Adverse Events

6.6.6.1 Dose Modification for V937 and/or Pembrolizumab due to Drug-related AEs in Arm 2 Part I

The CTCAE v5.0 must be used to grade the severity of AEs. The investigator may attribute toxicity events to the combination of V937 and pembrolizumab (since one may not be able to separate individual drug effects in every circumstance) and modify the dose according to [Table 17](#). If a dose modification for toxicity occurs with V937, the dose may not be re-escalated to the dose that preceded the dose modification. Dose modifications are always based on the previous cycle.

Reduction or holding of 1 agent and not the other agent is appropriate if, in the opinion of the investigator, the toxicity is clearly related to 1 of the study interventions. For example, if V937 is held due to an AE attributed to that drug, then pembrolizumab may continue to be administered. Appropriate documentation is required regarding to which drug the investigator is attributing the adverse event. If, in the opinion of the investigator, the toxicity is related to the combination of 2 agents, then both drugs should be held according to recommended dose modifications.

The dose of V937 may be decreased during Arm 2, Part I (as described in [Table 17](#)). Participants may receive up to 2 dose modifications of V937 during the dose escalation phase, provided this reduction is not lower than that specified in DL1 ([Table 13](#)). If a dose reduction is needed from DL1, then V937 treatment should be discontinued. If further toxicity occurs, or criteria for resuming treatment are not met, then the participant must also be discontinued from study. If a participant experiences several toxicities which result in conflicting therapeutic regimens, then the treating physician should adhere to the most conservative dose adjustment recommended (ie, adjustment based on the severest AE reported). There will be no V937 dose reductions in Arm 1 or Arm 2, Part II.

Exceptional circumstances to the dose modification tables may be considered after consultation with the Sponsor.

Table 17 V937 Dose Modification and Treatment Discontinuation Guidelines for Drug-related Adverse Events in Arm 2, Part I (mTPI)

Toxicity	Hold Treatment	Criteria for Restarting Treatment	V937 Dose for Restarting Treatment	Criteria for Discontinuation after Consultation with Sponsor
Hematological toxicities:				
• Any Grade 1 hematological toxicity	No	N/A	N/A	N/A
• Any Grade 2 hematological toxicity, or Grade 3 toxicity that persists for \leq 5 days	Per medical assessment of the investigator	If treatment held, may be restarted when AE resolves back to baseline or to Grade 1.	Per medical assessment of the investigator: may decrease dose by 1 dose level.	If AE persists for 12 weeks without resolution following reduction in dose
• Any Grade 3 hematologic toxicity that persists for $>$ 5 days, or Grade 4 hematological toxicity • Febrile neutropenia • Grade 3 thrombocytopenia of any duration if associated with bleeding	Yes	Treatment may be restarted when AE resolves back to baseline or to Grade 1.	Decrease dose by 1 dose level.	If AE persists for 12 weeks without resolution following reduction in dosing schedule. Permanent discontinuation should be considered for any severe or life-threatening event
Nonhematological toxicities:				
• Any Grade 1 nonhematological toxicity • Grade 2 alopecia • Grade 2 fatigue	No	N/A	N/A	N/A
• Any Grade 2 nonhematological toxicity except Grade 2 alopecia and Grade 2 fatigue	Per medical assessment of the investigator	If treatment held, may be restarted when AE resolves back to baseline or to Grade 1.	Per medical assessment of the investigator: may decrease dose by 1 dose level.	If AE persists for 12 weeks without resolution following reduction in dose.
• Any Grade 3 or 4 nonhematological toxicity (not including laboratory, unless clinically significant medical intervention is required to treat the participant, or the abnormality leads to hospitalization, or the abnormality persists for $>$ 1 week)	Yes	Treatment may be restarted when AE resolves back to baseline or to Grade 1.	Decrease dose by 1 dose level.	If AE persists for 12 weeks without resolution following reduction in dose. Permanent discontinuation should be considered for any severe or life-threatening event

In case toxicity does not resolve to Grade 0-1 within 12 weeks after last intervention, V937 should be discontinued after consultation with the Sponsor.

With investigator and Sponsor agreement, participants with a laboratory AE still at Grade 2 after 12 weeks may continue intervention in the study only if asymptomatic and controlled.

After any Grade 4, drug-related AE, participants should not restart study intervention without consultation with the Sponsor. Toxicity must have resolved to Grade 0-1 or baseline prior to restarting.

Pembrolizumab treatment will be modified for the irAEs described in Section 6.6.2.

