6.6 Dose Modification (Escalation/Titration/Other) [Arm 1 and Arm 2 (Part I & II)]

Adverse events (both nonserious and serious) associated with V937 and pembrolizumab exposure may represent an immunologic etiology. These AEs may occur shortly after the first dose or several months after the last dose of treatment.

The CTCAE v5.0 must be used to grade the severity of AEs. The investigator may attribute each toxicity event to V937 alone, to pembrolizumab alone, or to the combination, and modify the dose according to [Table 14](#).

Reduction or holding of 1 agent and not the other agent is appropriate if, in the opinion of the investigator, the toxicity is clearly related to 1 of the study interventions. For example, in combination, if V937 is held due to an AE attributed to that drug, then pembrolizumab may continue to be administered, and vice versa. Appropriate documentation is required regarding to which drug the investigator is attributing the AE. If, in the opinion of the investigator, the toxicity is related to the combination of 2 agents, then both drugs should be held according to recommended dose modifications.

Pembrolizumab or V937 may be interrupted for situations other than treatment-related AEs such as medical/surgical events or logistical reasons not related to study therapy. Participants should be placed back on study therapy within 3 weeks of the scheduled interruption, unless otherwise discussed with the Sponsor. The reason for interruption should be documented in the participant's study record.

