6.6.1 Dose Modification for V937

The most common drug-related adverse reactions seen with V937 treatment are fatigue, chills, pyrexia and influenza-like illness. These events are mainly Grade 1 or 2 in severity, transient, and easily managed.

Treatment-related AEs specific to V937 ITu administration include injection site pain, erythema, pruritis, discharge and edema reactions. These AEs are largely risks associated with performing an intralesional injection procedure and have not been reported when V937 has been administered via IV or intravesicular routes. These symptoms have been largely mild in their severity (ie, Grade 1 or 2).

As common practice, anti-inflammatory or anti allergic agents, such as acetaminophen or ibuprofen, should be initiated if Grade 2 fever, chill, or site injection reaction occurs.

Permanently discontinue V937 if these Grade 3 AEs reoccur in the same participants or are > Grade 3. For other instances in which dose interruption(s) may be required, discuss with Sponsor.

Within-participant dose escalation is not permitted.

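### Table 17 leaves open a V937 restart after a Grade 4 fever, chill or injection-site reaction at DL2 or DL3, where Section 6.6.1 requires a permanent stop

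*Combined protocol and SAP*

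**What the plan says.** Two parts of Section 6.6 deal with V937 after a reaction to the injection.

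- **Section 6.6.1.** The heading of its parent, Section 6.6, names Arm 1 and both parts of Arm 2, so 6.6.1 applies to Arm 2 Part I. It says that anti-inflammatory or anti-allergic agents "should be initiated if Grade 2 fever, chill, or site injection reaction occurs". It then orders: "Permanently discontinue V937 if these Grade 3 AEs reoccur in the same participants or are > Grade 3". Other situations that may need a dose interruption are left to discussion with the Sponsor.
- **Section 6.6.6.1 and Table 17 (Arm 2 Part I only).** One row takes every drug-related Grade 3 or 4 nonhematological toxicity, apart from laboratory findings without clinical consequence. Treatment is held, then: "Treatment may be restarted when AE resolves back to baseline or to Grade 1". The restart dose is one level lower. On stopping for good, the row says: "Permanent discontinuation should be considered for any severe or life-threatening event". A note under the table adds: "After any Grade 4, drug-related AE, participants should not restart study intervention without consultation with the Sponsor". The text before the table says: "Participants may receive up to 2 dose modifications of V937 during the dose escalation phase". It sets DL1 as the floor: a participant who would need a reduction from DL1 stops V937.

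Section 7.1 lists, among the reasons for which study intervention must be discontinued, any related toxicity that Section 6.6 specifies as a reason for permanent discontinuation. Section 4.1 sends the reader to Sections 6.6.5 and 6.6.6.1 for the DLT definition and the V937 dose-modification criteria, and does not mention 6.6.1. The text under Table 17 points elsewhere for pembrolizumab ("Pembrolizumab treatment will be modified for the irAEs described in Section 6.6.2") but gives no such pointer to 6.6.1 for V937.

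**The concern.** The same event in the same participant meets a mandatory stop in one section and a conditional restart in another. Table 17 makes no exception for the reactions in Section 6.6.1 and has no recurrence rule, and Section 4.1 directs sites to it. A Part I site working from the table could re-inject a live virus into a liver lesion after a reaction that Section 10.3.5 grades as life-threatening, although 6.6.1 says V937 is over for that participant. Section 4.3.1.1 states that V937 had not previously been injected into visceral tumors, so this is the setting where the stopping rule most needs to be clear. What is at stake is participant safety and consistent handling of the event.

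**Working it through.** No power or error-rate calculation applies. The check is to run both rules for each starting dose level and event, and then count the doses at stake.

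**Inputs**
- Dose levels: DL1 3 × 10⁷, DL2 1 × 10⁸, DL3 3 × 10⁸ TCID₅₀ maximum per participant (Section 4.1.2, Table 13).
- Maximum of 9 V937 doses in Arm 2 (Section 4.1.2).
- Table 17: one level down per Grade 3 or 4 event. Section 6.6.6.1: at most two modifications, with DL1 as floor.
- Section 6.6.1: permanent stop above Grade 3 or at a recurrent Grade 3, for the reactions it covers.

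**Outcome for a fever, chill or injection-site reaction**

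| Starting level | Event | Section 6.6.1 | Table 17 with Section 6.6.6.1 | Conflict? |
|---|---|---|---|---|
| DL3 | Grade 4 | stop | restart at DL2 possible after Sponsor consultation | yes |
| DL2 | Grade 4 | stop | restart at DL1 possible after Sponsor consultation | yes |
| DL1 | Grade 4 | stop | stop (floor) | no |
| DL3 | second Grade 3 | stop | first event to DL2, second to DL1 (2 modifications) | probable |
| DL2 | second Grade 3 | stop | first event to DL1, second stops (floor) | no |
| DL1 | first Grade 3 | no stop ordered | stop (floor) | no: V937 has ended before 6.6.1 would apply |

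**Why the DL3 second-Grade-3 row is only probable.** Straight after the DL1 floor, Section 6.6.6.1 says that if further toxicity occurs, or the criteria for resuming are not met, the participant must also leave the study. If that covers further toxicity after any reduction, the second Grade 3 ends participation and both texts agree. If it covers only participants who have already stopped V937 at DL1, the second step-down stands. The second reading fits the allowance of two modifications better, but the text does not settle it. The Grade 4 rows do not depend on it.

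**Doses at stake (upper bounds)**
- Remaining doses = 9 − doses already given.
- Grade 4 at dose 1: 9 − 1 = 8 further doses under Table 17, each up to 1 × 10⁸ TCID₅₀ from a DL3 start or 3 × 10⁷ from a DL2 start. Under 6.6.1: 0.
- Grade 3 at doses 1 and 2, DL3 start, second step-down allowed: 9 − 2 = 7 further doses, each up to 3 × 10⁷ TCID₅₀. Under 6.6.1: 0.

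Doses missed while treatment is held would lower the 8 and the 7.

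**The case against.** The strongest reply is that the protocol, read as a whole, already gives one answer. Section 7.1 makes a permanent stop specified anywhere in Section 6.6 binding. Table 17 is only permissive, so a site that stops V937 breaches nothing, while a site that restarts breaches 6.6.1 and 7.1. This stands as far as it goes: it shows which rule should prevail. It does not change the table that Section 4.1 names for V937 dose modification, and that table still offers the restart. The rule in 6.6.6.1 to follow the most conservative adjustment does not help, because it concerns several toxicities in one participant and not two rules for one toxicity.

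Other replies stand in part:

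- **Sponsor consultation.** A Grade 4 restart cannot happen without it. This is a real safeguard and makes divergent handling between sites less likely. It remains a route to restart that 6.6.1 does not provide.
- **Which reactions are meant.** Section 6.6.1 says *these* Grade 3 AEs without having named any Grade 3 event. The sentence before it supports fever, chill and injection-site reaction, but fatigue and influenza-like illness also appear earlier in the section. The event list is an inference.
- **Signposts.** They do not all point to Table 17. Sections 6.6.3.1 and 8.4.7 refer to 6.6.1 for V937 dose-interval modification, though in the context of hepatic events.
- **Reach.** Section 6.6.1 describes these reactions as mainly Grade 1 or 2, and the study is being discontinued.

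**Conclusion.** The conflict is in the text. It is firm for a Grade 4 reaction at DL2 or DL3 and probable for a second Grade 3 reaction after a DL3 start. It rests on reading Section 6.6.1 as covering Part I, which its parent heading supports, and on taking *these* reactions to be those in the preceding sentence. Its size is up to 8 further doses against 0 in the firm case and up to 7 against 0 in the probable one.

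Three stronger readings are tempting and not supported:

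- **That the protocol as a whole authorises the restart.** Section 7.1 says otherwise; the fault lies in Table 17 followed literally.
- **That such cases can be expected with some stated frequency.** The documents give no Grade 3 or 4 rates for these reactions and do not fix how many participants reach DL2 or DL3. Any probability would only restate the rate assumed.
- **That the Arm 2 endpoint of discontinuation due to an AE, or the RP2D, would be materially distorted.** Nothing in the documents shows this. Stop rules already differ between Parts I and II by design, since reductions are allowed only in Part I.

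The correction is worth making because it is cheap and the permissive reading carries the participant risk. Its practical reach is limited: the study is closing, and the documents do not say how many Part I participants still receive V937.

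**What to change.** Add one line to Table 17: *For the reactions covered by Section 6.6.1, any event above Grade 3 or a recurrent Grade 3 event requires permanent V937 discontinuation; no restart at a lower dose level.* In Section 6.6.1, replace the loose reference with a list of the reactions meant, so that the Table 17 line neither narrows nor widens the sponsor's intent. The stop at DL1 stays as it is. The DLT definition, the endpoints and the analysis need no change.

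The cost is two small text edits. For these reactions, participants at DL2 or DL3 lose a restart after Grade 4, and those who started at DL3 lose a second step-down after a repeated Grade 3. Section 6.6.1 already excludes both.
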